Oregon Health & Science University RESEARCH PROTOCOL

Protocol Title:

Evaluating Community Health Centers' Adoption of a New Global Capitation Payment (eCHANGE)

Principal Investigator:

[name]

Assistant Professor, Oregon Health & Science University Department of Family Medicine
[name]
[name]

[contact]

Sponsor:

Robert Wood Johnson Foundation, grant #71125
Agency for Healthcare Research and Quality (AHRQ)

Specific Aims:

Aim 1: Assess pre-post Alternative Payment Methodology (APM) changes in internal services utilization and quality of clinical care delivered in intervention sites, as compared with control sites.

Hypothesis 1a: Patterns of internal services utilization (e.g., face-to-face visits, e-mail visits) will change among intervention clinics' patients from pre- to post-APM, while control clinics' patients' rates will not change.

Hypothesis 1b: Intervention site patients will achieve greater pre-post improvements in quality of care delivered internally, as compared to the rates of improvement for patients in control clinics.

Aim 2: Measure pre-post changes in patients' utilization of external services (e.g., emergency department) and overall costs to the Medicaid program among patients from intervention clinics, as compared to patients from control clinics.

Hypothesis 2a: Expenditures attributed to external services will decrease for patients from intervention clinics, but these expenditures will remain the same or increase for patients in the control clinics.

Hypothesis 2b: Total Medicaid expenditures will decrease for patients from intervention clinics, while expenditures for patients from control clinics will remain the same or increase.

Aim 3: Study the change processes associated with APM implementation, including the organizational, workflow, and service delivery changes made in the Community Health Centers (CHCs) during and after APM implementation.

Hypothesis 3a: APM clinics will make fundamental pre-post changes in patterns of clinical care delivery and staff workflow.

Hypothesis 3b: There will be variability among the intervention clinics in what changes are successfully achieved, associated with vision, approach, strategic planning, and other clinic characteristics.

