Analysis Plan. We will begin qualitative analyses shortly after data collection commences. The study team will meet regularly to review all data, and listen to and discuss key segments of the recorded interviews. Analyzing qualitative data as it is collected is crucial to monitoring data quality, refining observation and interview guides, and monitoring theme saturation. This ongoing process will be used to track emerging themes and create a coding template to be used for more in-depth analysis. We will follow the 5-phase analysis strategy described by Miller and Crabtree (describing, organizing, connecting, corroborating/ legitimizing, representing).^{34,35} We will use an immersion-crystallization approach in which the team reads and discusses the data for each clinic (immersion) to identify key findings (crystallization);^{35,36} we will do this twice, first to identify key themes within each “case” CHC, and then to identify cross-case finding.

The survey data and interview transcripts will be coded using the 5-phase analysis strategy explained above. We will also analyze differences between the Phase I and Phase II clinics’ experiences with APM implementation.

Quantitative data collection

We will compile EHR and Medicaid claims datasets that include data from up to 3 years pre-APM implementation, during implementation, and ≥ 3 years post.

Aims 1 and 2 Evaluation Summary				
Evaluate effect of APM intervention on:	Study Time Periods	Data Sources	Inclusion Criteria	Analyses
Aim 1. Internal services utilization and quality of care delivered; Aims 2 & 3. Utilization of and spending on services outside of the CHC,	Up to 3 years pre-APM implementation; ≥ 3 -years post-APM implementation;	1. Internal services: OCHIN EHR data 2. External services and expenditures:	1. Total clinic population: established patients at intervention and control clinics aged 2-64 2. Medicaid	Clinic level analysis using the DID analysis and patient level analysis using Generalized Estimating Equation models, to accommodate serial and intra-clinic correlations, categorical and continuous covariates, fixed and time-dependent covariates. Two-part models will be used to accommodate distributions

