on utilization of CHC services and other recommended care, and the resulting effect on external services utilization and overall cost of care. The primary independent variable is whether or not the patient was exposed to the APM by being a patient at an intervention vs. control site (an *enabling / hindering factor*). The *primary dependent variables* of utilization of internal / external services and quality of care delivered are based on (i) the Medicaid initial core sets of health quality measures for adults,^{43,44} and (ii) pediatric care quality measures developed by AHRQ's National Advisory Council Subcommittee on Children's Healthcare Quality Measures for Medicaid and CHIP Programs, pursuant to the Children's Health Insurance Program Reauthorization Act. We will select measures that are: 1) identified by Oregon's Medicaid program and/or those on the list of Clinical Quality Measures and other EHR incentive programs;^{45,46} 2) feasibly measured with EHR or Medicaid claims data (**our team has created methods for adapting quality measures based on claims data for use in OCHIN's EHR data^{47,48}**); 3) representative across age groups and gender; 4) representative of treatment levels (e.g., prevention, acute and chronic condition care); and 5) relevant to CHC populations. With guidance from an expert advisory group, we will select and define final specifications and modify them to accommodate calculation over the pre-post periods. Assessment of internal services utilization and quality can be done using OCHIN's EHR data; assessment of external services utilization will use EHR data linked with Medicaid administrative data.

Statistical analyses. We will conduct analyses at the clinic- and patient-level. The clinic-level analyses are typically performed in cluster-randomized trials, and the individual-level analyses are typically performed in observational studies in order to account for socio-demographic differences among clinics.

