Clinic-level: We will summarize baseline measures using descriptive statistics and data visualization methods (e.g., histograms, scatter plots) to assess how baseline data differs. To compare pre- and post-APM rates, we will assess data in pre- and post-APM time periods, using regression methods to estimate pre- vs. post-intervention change for each clinic. We will use a Generalized Estimating Equation (GEE) approach to adjust for serial correlation and other potential confounders. The pre- vs. post-APM changes will be calculated with GEE logit regression between intervention and control CHCs (DID analysis). Additional analyses to account for differences among APM phases and temporal inclusion may be used.

Patient-level: The primary independent variable is whether a patient belongs to an intervention or control CHC. Other covariates include predisposing factors and need for services. We will use GEE models^{49,50} which offer flexible regression modeling to accommodate different sources of correlations (serial, intra-clinic, and intra-family), categorical and continuous covariates, and fixed and time-dependent covariates. These methods offer a wide range of parametric distributions to model the dependent variables, including logistic regression (binary data), beta regression (percent data), Poisson regression (count data), and Gaussian regression (normally distributed data). For example, to assess a change in quality rates, a GEE logistic regression model can analyze quality of care received in pre- and post-APM periods as a function of whether a patient belongs to an intervention or control CHC and other possible confounders (e.g., predisposing factors; need for services). Serial, and intra-clinic correlations will be modeled, and empirical robust standard errors will be applied, to provide valid inference.⁵¹ As an exploratory secondary analysis, we will evaluate the impact of the APM intervention on total number of recommended services received. The distribution of the total services received will be examined first before selecting a specific model to use for the analysis. Analytic models will be refined through an iterative process, guided by the hypotheses, conceptual model, and preliminary analyses. If there are significant patient differences between the intervention and control sites, we may use propensity score methods in the analysis phase to reduce the observed bias and adjust for imbalances between intervention and control clinics.⁵²

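### Does the patient-level Aim 1 model leave out the group-by-period term that Hypotheses 1a and 1b need?

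*Combined protocol and SAP*

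**What the plan says.** Specific Aims sets the target. Hypothesis 1b is that "Intervention site patients will achieve greater pre-post improvements in quality of care delivered internally" compared with control patients. Hypothesis 1a begins "Patterns of internal services utilization (e.g., face-to-face visits, e-mail visits) will change among intervention" and adds that control rates stay as they were. Both are statements about change over time in one arm set against the other.

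Study variables says: "The primary independent variable is whether or not the patient was exposed to the APM by being a patient at an intervention vs. control site". The patient-level paragraph under Statistical analyses repeats the idea ("The primary independent variable is whether a patient belongs to an intervention or control CHC") and lists predisposing factors and need for services among the other covariates. Its example opens "For example, to assess a change in quality rates, a GEE logistic regression model". The remainder of that sentence sets out what is fitted, namely that this approach "can analyze quality of care received in pre- and post-APM periods as a function of whether a patient belongs to an intervention or control CHC", with possible confounders alongside. The paragraph ends with a general rule: "Analytic models will be refined through an iterative process, guided by the hypotheses, conceptual model, and preliminary analyses".

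The Analyses column of the Aims 1 and 2 Evaluation Summary reads: "Clinic level analysis using the DID analysis and patient level analysis using Generalized Estimating Equation models". The clinic-level paragraph is labelled as a difference-in-differences (DID) analysis. Econometric analyses defines the DID for spending as the marginal effect on the product of a post-APM indicator and an intervention-clinic indicator.

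**The concern.** Taken word for word, the patient-level example regresses outcomes from both periods on clinic group and confounders. Pooled over periods, the group coefficient is not a DID. It contains any baseline difference between arms and only part of any APM effect. If the arms have different shares of post-APM observations, it also contains part of the secular trend. Unequal shares are possible, because the quantitative Inclusion criteria section says panels may change between periods and face-to-face visits may fall.

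An analyst who fitted that model could report a pre-existing gap as an APM effect, or understate a real one. The patient-level Aim 1 result could then disagree with the clinic-level DID for reasons unrelated to APM. The wording of the summary table, which attaches DID to the clinic level and GEE to the patient level, seems to support this reading.

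**Working it through.** The documents give no rates, effect sizes or post-period shares, so there is no planned figure to reproduce. Every rate and share below is an assumption.

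**1. What a group-only fit would estimate.** On the linear scale, let *gap* be the baseline difference (intervention minus control), *trend* the control change, and wI and wC the post-APM shares of observations in the two arms.

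- Control mean = c0 + wC × trend
- Intervention mean = c0 + gap + wI × (trend + DID)
- Group coefficient = gap + wI × DID + (wI − wC) × trend

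Results:

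| Control pre/post | Intervention pre/post | wC / wI | Group only | Interaction |
|---|---|---|---|---|
| 60 / 60% | 60 / 64% | 0.5 / 0.5 | 0.5 × 4 = 2.0 points | 4.0 points |
| 60 / 60% | 60 / 64% | 0.3 / 0.3 | 0.3 × 4 = 1.2 points | 4.0 points |
| 50 / 60% | 50 / 60% | 0.5 / 0.7 | 0.2 × 10 = 2.0 points | 0 |
| 60 / 65% | 60 / 69% | 0.5 / 0.4 | 0.4 × 4 − 0.1 × 5 = 1.1 points | 4.0 points |

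On the logistic scale with equal shares:

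- 60% against 65% in both periods: group OR = (0.65/0.35)/(0.60/0.40) = 1.24; interaction OR = 1.00.
- Controls flat at 60%, intervention 60 to 64%: pooled 62% against 60% gives OR = (0.62/0.38)/(0.60/0.40) = 1.09; interaction OR = (0.64/0.36)/(0.60/0.40) = 1.19.

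A period main effect alone removes the trend part but not the gap or the dilution. In the last table row it gives 1.8 points. With 60/65% against 65/70% at shares 0.5/0.4 it gives 5.0 points, although the DID is zero.

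A simulation agrees. It assumed 40 clinics, 60 patients per clinic and period, clinic SD 0.3 logits, a baseline gap of 0.4 logits, zero DID and 200 replicates. The group-only coefficient averaged 0.392 and was significant at 5% in 93% of replicates. The interaction averaged 0.001 and was significant in 6.5%.

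So the arithmetic behind the concern is right. What remains is whether the plan prescribes that fit.

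**2. What the plan prescribes, read together.**

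- *The example's own sentence.* It is offered to assess a change in quality rates and names both periods. If the quantity modelled is change, group is the right main regressor and its coefficient is the DID. In the last table row, controls change by 5 points and intervention by 9, and 9 − 5 = 4. The longitudinal cohort of the same patients, planned for some comparisons, allows exactly that.
- *Its status.* It is introduced as an example of what a GEE model can do, and its lists of covariates and confounders are open-ended. The paragraph also allows time-dependent covariates. It is not a model equation.
- *The design.* Subjects and Experimental Design couples DID with the matched design at either level.
- *The governing rule.* Models are refined according to the hypotheses, and H1a and H1b are group-by-period statements.
- *The shorthand.* Study variables applies the same group-exposure label to external services as well as internal ones. Econometric analyses then writes the interaction for spending, alongside the same patient covariates. The label therefore does not mean that period and interaction are left out.
- *The summary table.* The row also covers the external-services and spending analyses, for which the plan writes out a DID on individuals. Its wording therefore cannot mean that patient-level analyses exclude DID.

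**The case for a change.** The best case for a change is that the omission is specific to one analysis. The clinic-level text is labelled DID and the spending text spells out the interaction. The patient-level Aim 1 text does neither, does not refer across to Econometric analyses, and offers this example as its only model. Matching or propensity scores may shrink a baseline gap but do not remove the dilution. Refinement guided partly by preliminary analyses is a reason to fix the parameter beforehand. A sentence or two would settle it, with no new data or methods.

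What stands is that the paragraph does not write out the period and group-by-period terms. What does not stand is that it contradicts the DID design. That needs an open-ended illustration to be read as a complete specification, against its own stated purpose and the rest of the plan.

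The obvious added sentence, naming the interaction as the test of both hypotheses, would itself be incomplete. H1a also says control rates do not change, which an interaction does not test. The sentence would also need a reporting scale, because Modeling interaction terms already warns that the interaction coefficient in a non-linear model is not the effect itself.

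**Conclusion.** No change to the plan follows. The patient-level Aim 1 paragraph is under-specified, but the hypotheses, the design statement, the refinement rule and the spending model all point to the same contrast. A competent analyst following them will fit group, period and their product, or model change by group. Writing this down would record the analysis already intended and would not alter it.

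The exposure is limited to the patient-level Aim 1 results. The confounder-adjusted clinic-level DID addresses the same hypotheses in any case. The distortions computed above, such as an odds ratio of 1.24 in place of 1.00 or 2 points in place of 4, would arise only if someone fitted the group-only model. They rest entirely on assumed rates and shares and say nothing about how likely that is here. The conclusion assumes that the analysts read the patient-level paragraph together with the hypotheses and the design section, as the plan tells them to.

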We will utilize a mixed-methods approach, drawing upon both qualitative and quantitative data from clinic site visits, clinic surveys, key informant interviews, follow-up calls, Medicaid administrative claims, and the OCHIN electronic health record (EHR).

Background and Significance:

The common practice of reimbursing primary care providers through a fee-for-service model hampers efforts to develop patient-centered medical homes: it rewards a high volume of face-to-face clinic visits, which does not necessarily lead to value, quality, and patient-centered care. This is especially problematic in Community Health Centers (CHCs), which are currently paid based on the Prospective Payment System (PPS) rate, a fee-for-service model. To reform this payment model in CHCs, Oregon developed an Alternative Payment Methodology (APM) that converts PPS (Medicaid revenue) to a prospective, capitated per-member per-month rate. The Oregon Primary Care Association (OPCA) is providing technical assistance to the APM clinics, with funding from the Robert Wood Johnson Foundation. The APM project seeks to (i) incentivize providing value over volume of visits, (ii) support comprehensive treatment modalities for patients with complex needs, and (iii) allow CHCs to focus more of their resources on population health initiatives.

APM is being implemented in several phases. Three CHC organizations are participating in Phase I of the APM demonstration project, which kicked off on March 1, 2013. Five additional CHC joined Phase II July 1, 2014 or October 1, 2014. Phase III began July 1, 2015 with three additional CHC organizations. Each CHC organization may include several clinics. All but one of the APM CHCs are members of the OCHIN community health information network practice-based research network, with a single, shared EHR. In this study, we propose to evaluate the APM clinics and/or patients matched to an equal number of control clinics and/or patients that are part of the OCHIN network.

Preliminary Studies / Progress Report:

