We will also assemble a dataset of EHR data on approximately 400,000 patients aged 2-64 from the implementation clinics and/or patients and control clinics and/or patients. All Phase I study sites have agreed to take part in the initial qualitative data collection portion of this study and have agreed to \$1000 compensation at the organization level for their participation. We will select control sites and/or patients based on matching algorithms to ensure selected controls are similar to implementation clinics and/or their patients.

We will conduct up to two site visits to intervention clinics to observe practice changes that occurred post APM-implementation. We will also conduct preliminary qualitative data collection in the APM sites, including a practice survey and key informant interviews. Due to a shortage of funding for the initial baseline data collection, and because the Phase II and III sites have limited involvement in the study, they will not receive reimbursement for study participation.

Baseline qualitative data collection

Box 1: Qualitative Activities, Subjects and Recruitment			
Study Site Name	Study Activities	Approximate Number of Clinic Staff Subjects at Each Site	Recruitment Strategy
Phase I APM Sites: Virginia Garcia – Beaverton, Cornelius, Hillsboro, McMinnville (several clinics may be included at each of these locations)	Pre-site visit telephone interview	1	Clinic “point-person”
	Phone interview after monthly OPCA meeting, if needed	2	Clinic “point-person”
	Staff interviews	10	Referred by clinic “point-person” and identified by study staff during site visit
	Practice Change Assessment Questionnaire	20	Clinic staff meeting attendees
OHSU Richmond (several clinics may be included from this location)			
Oregon Primary Care Association Office	Observe monthly meetings	10	Monthly project meeting attendees
Phase II APM Sites: OHSU Scappoose (several clinics may be included from this location)	Telephone interview	1	Clinic “point-person”
	Phone interview after monthly OPCA meeting, if needed	2	Clinic “point-person”
	Practice Change Assessment Questionnaire	20	Clinic staff meeting attendees
Coastal Family Health			

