Econometric analyses. Using difference-in-differences methods, we will calculate the average pre-post APM difference in spending of patients in APM intervention clinics, subtracted by the average difference among patients in comparison clinics. Changes in spending after APM implementation in the intervention

clinics vs. spending changes in the control clinics will “net out” any secular changes not related to APM. Any remaining significant differences in outcome – the DID – are attributed to the APM intervention. These findings will help to assess whether the APM intervention can help reduce costs, and if so, whether the reduction comes from lower spending at the CHC level or through reductions in potentially unnecessary or inefficient use of specialty and hospital services. We note that CHCs are not financially at risk for services outside of the CHC and thus do not have incentives to act as gatekeepers to care. Thus, reductions in spending for specialty services and other external services would most likely reflect improvements in internal care delivery.

Analytically, the difference-in-differences estimate is represented by the marginal effect on the interaction between a dummy variable indicating that the observations occur in the post-APM period and a dummy variable indicating the individual’s attribution to an APM intervention clinic. We will also include patient-level variables to account for predisposing factors and need for services. A variety of issues must be addressed in our DID estimation:

Definition of external services. External services will be defined as any care occurring outside of the CHC, e.g., emergency department visits, hospitalizations, and other ambulatory care that takes place in settings other than the CHC.

Accounting for clinic-level effects. Our study will focus on the “treatment-effect” of the APM: how does the transition to a capitated payment system affect health care spending? Since this is our main focus, our approach may include use of clinic-level fixed effects to net out any time-invariant differences in clinic-level cost outcomes. However, recognizing the potential interest in clinic-level effects, in secondary analyses we will test hierarchical (mixed) models to more specifically model (i) clinic-level variation and (ii) patient-level variation.

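### The payment model is adopted mainly by CHC organization (about 10 in OCHIN), but the plan allows for correlation only up to the clinic, with no few-cluster correction and no defined bootstrap block, so DID intervals are too narrow if clinics of one organization change together

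*Combined protocol and SAP*

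**What the plan says.** Background and Significance describes APM adoption by organization: three CHC organizations in Phase I, then "Five additional CHC joined Phase II July 1, 2014 or October 1, 2014", then three more in Phase III. It adds that "Each CHC organization may include several clinics" and that "All but one of the APM CHCs are members of the OCHIN community health information network practice-based research network".

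Every statement about correlation stops at the clinic:

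- The Aims 1 and 2 Evaluation Summary plans a "patient level analysis using Generalized Estimating Equation models, to accommodate serial and intra-clinic correlations".
- Statistical analyses, Clinic-level, uses GEE to handle serial correlation and treats clinics as the units.
- Statistical analyses, Patient-level, lists serial, clinic and family correlation and concludes: "Serial, and intra-clinic correlations will be modeled, and empirical robust standard errors will be applied, to provide valid inference". It states no small-sample correction.
- Econometric analyses, Accounting for clinic-level effects, allows optional clinic fixed effects and says "in secondary analyses we will test hierarchical (mixed) models to more specifically model (i) clinic-level variation and (ii) patient-level variation".

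For spending, Modeling interaction terms takes the 95% interval from a bootstrap without naming what is resampled. Accounting for repeated observations lists a block bootstrap as one option to consider, in the context of repeated observations on each individual, and does not define the block.

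**The concern.** Phases and start dates follow the organization. The qualitative analysis treats the CHC as the case, and Hypothesis 3b links change to vision and strategic planning. It is therefore plausible that clinics of one organization move together from before to after APM. A variance clustered on clinics counts them as independent and overstates the information. A plain sandwich with few clusters adds a further downward bias.

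The stakes are direct: Econometric analyses attributes any significant DID that remains to APM. An interval that is too narrow can present chance differences between organizations as an effect of the payment model. With roughly 400,000 patients, organizations rather than patients are likely to limit precision.

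**Working it through.** The plan gives no power calculation, intraclass correlation or standard error, so there is no figure of its own to reproduce. The steps are a count, a closed form and a simulation.

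**1. Adopting organizations.** 3 + 5 + 3 = 11 (Background and Significance). Less the one outside OCHIN: 10. Box 1 names seven of them with 4, 1, 1, 1, 4, 6 and 4 locations, 21 in all. Its five Phase II entries match the text only if "Phase II APM Sites: OHSU Scappoose (several clinics may be included from this location") counts apart from the Phase I site "OHSU Richmond (several clinics may be included from this location"). The documents do not say whether the two share a parent.

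**2. Assumed layout.** Take one clinic per Box 1 location, plus 2 clinics for each of the 3 Phase III organizations (assumed): 21 + 6 = 27 clinics in 10 organizations. Controls are either mirrored (10 organizations, 27 clinics) or single-clinic (27 organizations). Let rho be the share of the variance of clinic change that is common to an organization. The documents give no value for rho.

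**3. Closed form.** For organizations of size n_g and n clinics in an arm, the true variance over the clinic-based variance is 1 + rho × (Σn_g²/n − 1).

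- Σn_g² = 16 + 1 + 1 + 1 + 16 + 36 + 16 + 4 + 4 + 4 = 99, and 99/27 − 1 = 2.67.
- Mirrored controls: SE ratio = √(1 + 2.67 rho) = 1.13, 1.34 and 1.53 at rho 0.1, 0.3 and 0.5.
- Single-clinic controls (half the excess): √(1 + 1.33 rho) = 1.06, 1.18 and 1.29.

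**4. Simulation.** Clinic change = √rho × organization term + √(1 − rho) × clinic term, both standard normal, with no effect; 40,000 replicates per cell. Type I error in %, nominal 5%:

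| Test | Controls | rho 0 | 0.05 | 0.1 | 0.3 | 0.5 |
|---|---|---|---|---|---|---|
| Clinic-clustered, z | mirrored | 5.9 | 7.7 | 9.5 | 16.6 | 23.0 |
| Clinic-clustered, z | single-clinic | 5.9 | 7.0 | 7.8 | 10.9 | 15.1 |
| Clinic-clustered, corrected, t | mirrored | 4.5 | 6.0 | 7.6 | 14.2 | 20.2 |
| Clinic-clustered, corrected, t | single-clinic | 4.5 | 5.4 | 6.2 | 8.9 | 12.7 |

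Clustering on the organization, over the same range of rho:

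- uncorrected: 7 to 10%;
- percentile bootstrap of whole organizations within arm (6,000 replicates, 999 draws): 7 to 10%;
- CR3 (each organization's residual sum divided by 1 − n_g/n) with t on organizations minus 2 degrees of freedom (18 or 35): 4.0 to 5.5%.

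Repeat runs of the main cells agreed to within about half a percentage point.

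**5. Sensitivity of the clinic-clustered z test.**

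- Merging the two OHSU sites moves it by less than 1 point.
- Giving each Phase III organization 1 or 4 clinics moves it by at most 1.2 points.
- Five control organizations give 11.0, 19.6 and 27.2% at rho 0.1, 0.3 and 0.5.
- Two clinics per location throughout give 13.5, 26.1 and 36.5% (mirrored) or 9.5, 17.0 and 23.7% (single-clinic).
- Organization-level CR3 with t stays at 3.9 to 6.4% in all of these.

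**The case against.** The strongest reply is that the harm is not shown from the documents. Without a correlation of change, a total clinic count or a number of control organizations, any error rate is hypothetical. At rho of 0 to 0.05 a corrected clinic-level test is close to nominal (4.5 to 6.0%). That stands. A reader might infer from the larger figures that the plan's intervals are known to be badly wrong. The documents do not support this, because those figures need a sizeable rho or more clinics per organization.

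Two technical points also stand. Naming the organization as the bootstrap block is not enough: the percentile interval errs at 7 to 10%, no better than the clinic-level z test at rho up to about 0.1. And the simulation used unadjusted normal change scores, not logistic GEE, two-part models, matching, covariates or staggered starts. Clinic dummies nested in organizations can also make a CR3 adjustment singular unless they are removed first.

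The unit is not perfectly clean either. Exposure in the econometric model is defined by clinic, and the two OHSU sites may or may not share a parent. This is a reason to state a counting rule, not to leave the level open.

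Other defences fail. Optional clinic fixed effects remove only time-invariant differences, not shared change. Iterative model refinement names no level. Comparing CHCs defines exposure, not the variance cluster. The quoted sentence cites a paper on sandwich covariance estimation, but the plan's text adopts no correction from it.

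A reader might also infer that the plan chose a wrong bootstrap block; it is undefined, not wrongly defined. Nor would clustering by organization remove confounding by organization-level changes that coincide with APM. The point concerns interval width only.

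**Conclusion.** The concern holds in conditional form and should be fixed. The mismatch between the level of adoption and the level of inference is plain in the text. Its consequence depends on shared pre-post change within organizations, which is plausible but not quantified. Under the assumed layouts of 10 intervention organizations with 27 clinics, nominal 5% error is about 6% at rho 0, 8 to 10% at rho 0.1 and 11 to 17% at rho 0.3. These figures are illustrations, not estimates for this study. A correction kept at clinic level suffices only if rho is small.

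**What to change.** **GEE and DID models** (Evaluation Summary; Statistical analyses, Clinic-level and Patient-level). Make the CHC organization the independent cluster, with a bias-corrected sandwich such as Mancl-DeRouen or CR3 and a t reference based on the number of organizations. If clinic fixed effects are used, apply the correction after removing them. State how sites under a common parent are counted, including a parent with two start dates. Report the numbers of intervention and control organizations once matching is done. Replace the closing claim of validity in the quoted sentence with the cluster level and correction. Clinic-level clustering may stay as a sensitivity analysis.

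**Spending** (Modeling interaction terms; Accounting for repeated observations). Define the resampling block as the whole organization within arm, and do not rely on the percentile interval alone. Base the reported interval on a few-cluster method: a delete-one-organization jackknife standard error with a t reference, a wild cluster bootstrap or an organization-level permutation test. Check by simulation that its error is near nominal in the two-part model.

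**Cost.** No new data collection: SAP wording, an organization identifier in the de-identified file, and some extra programming and checking. Intervals widen and power falls. In the simulation the organization-level CR3 interval was 1.14 times (mirrored) or 1.08 times (single-clinic) the clinic-level one at rho 0, 1.29 or 1.15 times at rho 0.1, and 1.55 or 1.27 times at rho 0.3.
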